Observation 4 hours after the morning dose	X											Section 9.6.1
Pregnancy test (all female subjects)	urine		serum	serum	serum	urine	serum	urine	serum	serum	serum	At telephone contacts, a urine pregnancy test will be performed with a home kit provided by the study site. Results will be reported to the site by telephone (Section 11.5.6).
Serum chemistry	X		X	X	X		X		X	X	X	Section 11.5.2
Hematology	X		X	X	X		X		X	X	X	Section 11.5.2
Coagulation	X								X	X		Section 11.5.2

Table 3-2 Study VX19-445-116: Treatment Period and Safety Follow-up Visit

Event/ Assessment ^a	Day 1 ^b	Day 3 ± 1 day	Day 15 ± 3 days	Week 4 ± 5 days	Week 8 ± 5 days	Week 12 ± 5 days	Week 16 ± 5 days	Week 20 ± 5 days	Week 24 ± 5 days	ETT Visit	Safety Follow-up ^c 28 (± 7) Days After Last Dose of Study Drug	Comments
Urinalysis	X								X	X		Section 11.5.2
AEs and SAEs	Continuous from signing of ICF (and Assent Form) through Completion of Study Participation											Section 13.1; completion of study participation is defined in Section 9.1.6.
Concomitant medications	Continuous from signing of ICF (and Assent Form) through Completion of Study Participation											Completion of study participation is defined in Section 9.1.6.
Concomitant treatment and procedures	Continuous from signing of ICF (and Assent Form) through Completion of Study Participation											Completion of study participation is defined in Section 9.1.6.

Table 3-2 Study VX19-445-116: Treatment Period and Safety Follow-up Visit

[figure not shown]
[figure not shown]
Event/ Assessment ^a	Day 1 ^b	Day 3 ± 1 day	Day 15 ± 3 days	Week 4 ± 5 days	Week 8 ± 5 days	Week 12 ± 5 days	Week 16 ± 5 days	Week 20 ± 5 days	Week 24 ± 5 days	ETT Visit	Safety Follow-up ^c 28 (± 7) Days After Last Dose of Study Drug	Comments
Study Drug Administration												
ELX/TEZ/IVA or placebo	Day 1 through evening before Week 24 Visit											Administered within approximately 30 minutes of consuming fat-containing food (e.g., standard “CF” meal or snack) (Section 9.6.1). On scheduled visits, the morning dose of study drug will be administered at the site after predose assessments have been completed (food to be provided by site on these days).

AE: adverse event; CF: cystic fibrosis; [REDACTED]; ECG: electrocardiogram; ELX: elexacaftor; ETT: early termination of treatment; ICF: informed consent form; IVA: ivacaftor; SAE: serious adverse event; TEZ: tezacaftor

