9.1.6 Completion of Study Participation

Completion of study participation for each individual subject is defined as 1 of the following:

- For subjects who complete the Treatment Period and enter an open-label extension safety study within 28 days of the Week 24 Visit: the Week 24 Visit
- For subjects who complete the Treatment Period and do not enter an open-label extension safety study within 28 days of the Week 24 Visit: the Safety Follow-up Visit
- For subjects who prematurely discontinue study drug treatment but do not withdraw consent (and assent, as applicable): the latest of the Week 24 Visit, ETT Visit, or Safety Follow-up Visit (if required)
- For subjects who withdraw consent or assent: date of withdrawal of consent or assent, whichever is earlier (Section 9.9)

If subjects are lost to follow-up (Section 9.1.5) the date of completion of study participation will be defined as the date of the last contact the subject had with the site.

The end of study is defined in Section 13.2.8.

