9.6 Administration

9.6.1 Dosing

Study drug tablets will be administered orally as shown in Table 9-3. Subjects in both treatment groups (ELX/TEZ/IVA and placebo) will receive the same number of tablets each day to maintain the blind. Additional information is provided in the Pharmacy Manual.

Table 9-3 Study Drug Administration

Subject Weight at Screening	Tablet Strength	Time	Number of Tablets Taken
<30 kg	50-mg ELX/25-mg TEZ/37.5-mg IVA	AM	2 tablets
	75-mg IVA	PM	1 tablet
≥30 kg	100-mg ELX/50-mg TEZ/75-mg IVA	AM	2 tablets
	150-mg IVA	PM	1 tablet

ELX: elexacaftor; IVA: ivacaftor; TEZ: tezacaftor

Study drug should be administered with a fat-containing meal or snack, such as a standard “CF” meal or snack or a standard meal according to the following guidelines:

1. It is recommended that the dose be taken within approximately 30 minutes of the start of the meal or snack.
2. All doses of study drug (morning and evening, as applicable) should be administered at approximately every 12 hours (\pm 2 hours) on each dosing occasion (e.g., if the morning doses of study drug are administered at 08:00 hour on Day 1, all subsequent morning doses should be administered between 06:00 hour and 10:00 hour).
3. At the Day 1 Visit, all subjects will be observed for 4 hours after the morning dose of the study drug.
4. On days of scheduled visits, the morning dose of study drug will be administered at the site after predose assessments have been completed. The meal or snack will be provided by the site for the morning dose of study drug.
5. For visits after the Day 1 Visit, subjects will be instructed to bring all used and unused study drug to the site; study drug will be dispensed at each visit, as appropriate.
6. At the Week 24 Visit, the morning dose of study drug will NOT be administered. The last dose of study drug will be the evening dose administered the day before the Week 24 Visit.

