Vertex recommends that subjects and sites refer to local guidance regarding travel restrictions. There are no operational changes to the study protocols for subjects who can travel to the study sites for their visits. However, to ensure continued safety of subjects who *cannot* travel to the study sites for their visits (for any reason due to COVID-19), specific alternative measures are being implemented to minimize the risk of exposure to COVID-19 (see table below). As the COVID-19 pandemic evolves, Vertex will continue to assess the need for additional actions to ensure the safety of all involved in these clinical studies.

Addendum Version 3.0 summarizes additional measures taken for these ongoing CF clinical studies (see table below) to ensure continued safety.

Summary of Changes in Ongoing CF Clinical Studies for Subjects Who Cannot Travel to the Study Site

Protocol Change	Rationale for Change	Study Number
Addendum Version 3.0, dated 29 July 2020		

Assessments
 
Unscheduled visit(s) will be permissible at the discretion of the investigator(s) or Vertex. The unscheduled visit(s) may be conducted at any time during the study (including after the protocol defined last study visit) in the event assessments specified to be collected at a scheduled visit were not collected due to COVID-19.
	
To ensure subject safety and/or to facilitate evaluation of safety and/or efficacy if assessments are not performed per the schedule in the protocol due to COVID-19.
	
[REDACTED]
 
[REDACTED]
 
[REDACTED]
 
[REDACTED]
 
VX19-445-116
 
[REDACTED]

Implementaion of measures described in addenda versions 1.0 and 2.0, as applicable.
	
To ensure subject safety and/or to facilitate evaluation of safety and/or efficacy while maintaining study integrity and the safety of subjects and site personnel.
	
[REDACTED]

Summary of Changes in Ongoing CF Clinical Studies for Subjects Who Cannot Travel to the Study Site

Protocol Change	Rationale for Change	Study Number
Addendum Version 2.0, dated 15 May 2020		

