
Consenting of Subjects ICFs may be provided electronically or by post mail to subjects (and/or caregivers, as indicated per protocol). The subjects and/or caregivers will review the ICF with an appropriately qualified member of the investigator’s team via telephone contact or video call. After this review, subjects and/or caregivers will consent (or assent, if applicable), and/or re-consent verbally and by signing and dating the ICF and returning it to the site via post mail. The signed and dated ICF will then be signed and dated by the investigator.
 
Subjects participating in select studies may have the opportunity to enroll in longterm extension studies. Informed consent (or assent, if applicable), and/or re-consent for subjects (and/or caregivers, as indicated per protocol) may be obtained per the same process described above, as applicable.
	
To provide alternative methods of obtaining re-consent or consent, as applicable, while ensuring subject safety.
	
[REDACTED]
 
[REDACTED]
 
[REDACTED]
 
[REDACTED]

Study Drug Shipping Study drug may be shipped directly from the site to the subject, as applicable, and if permitted by local regulations; subject protected health information will not be released to Vertex.
 
Reconciliation, return, and destruction of study drug will continue to occur at the clinical site as indicated per protocol and in adherence to local regulations.
	
To ensure subjects can continue treatment with study drug without interruption while ensuring their safety.
 
To clarify that despite these alternative measures, reconciliation, return, and destruction of study drug will remain as indicated per protocol.
	
[REDACTED]
 
VX19-445-116

In-home Visits and/or Telephone Contact Study visits may be conducted as in-home visits by qualified personnel as requested by participating sites on a per-subject basis. In addition, all subjects may be contacted by site personnel by telephone or video call, irrespective of in-home visits.
	
To provide subjects the opportunity to continue participation in the clinical studies while ensuring their safety by minimizing the risk to COVID-19 exposure through travel.
	
[REDACTED]
 
[REDACTED]
 
[REDACTED]
 
for telephone contact only

Summary of Changes in Ongoing CF Clinical Studies for Subjects Who Cannot Travel to the Study Site

Protocol Change	Protocol Change	Protocol Change

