9 STATISTICAL ANALYSIS

9.1 General Considerations

Continuous variables will be summarized using the following descriptive summary statistics: the number of subjects (n), mean, SD, median, minimum value (min), and maximum value (max).

Categorical variables will be summarized using counts and percentages.

Baseline value, unless otherwise specified, will be defined as the most recent non-missing measurement (scheduled or unscheduled) collected before the first dose of study drug in the Treatment Period.

Absolute change from baseline will be calculated as post-baseline value – baseline value.

Relative change from baseline will be calculated as (post-baseline value – baseline value)/baseline value.

Treatment-emergent (TE) Period will include the time from the first dose date of study drug to 28 days after the last dose of the study drug or to the date of completion of study participation, whichever occurs first.

Unscheduled visits: Unscheduled visit measurements will be included in analysis as follows:

- 1) In scheduled visit windows per specified visit windowing rules
- 2) In the derivation of baseline and last on-treatment measurements
- 3) In the derivation of maximum and minimum values during TE period, and maximum and minimum change from baseline values during TE period for safety analyses
- 4) In individual subject data listings as appropriate

Visit windowing rules: The analysis visit windows for protocol-defined visits are provided in [Appendix A](#).

Incomplete/missing data will not be imputed, unless specified otherwise.

Outliers: No formal statistical analyses will be performed to detect or remedy the presence of statistical outliers, unless specified otherwise.

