12 LIST OF APPENDICES

Appendix A: Analysis Visit Windows for Safety and Efficacy Assessment

Table 12-1 Analysis Visit Windows for Safety and Efficacy Assessments			
Assessment	Visit¹	Target Study Day	Analysis Visit Window (in study days)^{2, 3, 4, 5}
Safety Assessment			
Serum Chemistry Hematology	Day 1 (Baseline)	1	≤1 Pre-dose
	Day 15	15	[1, 22]
	Week 4	29	(22, 43]
	Week 8	57	(43, 85]
	Week 16	113	(85, 141]
	Week 24	169	(141, 183]
	Safety Follow-up	Not applicable	Use nominal visit
Standard 12-lead ECG	Day 1 (Baseline)	1	≤1 Pre-dose
	Week 8	57	[1, 85]
	Week 16	113	(85, 141]
	Week 24	169	(141, 183]
	Safety Follow-up	Not applicable	Use nominal visit
Vital signs (excluding BMI, Weight and Height, and their z-scores) and pulse oximetry	Day 1 (Baseline)	1	≤1
	Day 15	15	[1, 22]
	Week 4	29	(22, 43]
	Week 8	57	(43, 85]
	Week 16	113	(85, 141]
	Week 24	169	(141, 183]
	Safety Follow-up	Not applicable	Use nominal visit
Coagulation	Day 1 (Baseline)	1	≤1 Pre-dose
	Week 24	169	[1, 183]
BMI, Weight, Height and the corresponding z-scores	Day 1 (Baseline)	1	≤1
	Day 15	15	(1, 22]
	Week 4	29	(22, 43]
	Week 8	57	(43, 85]
	Week 16	113	(85, 141]
	Week 24	169	(141, 183]
	Safety Follow-up	Not applicable	>183
Efficacy Assessment and Pharmacodynamic Assessment			

Table 12-1 Analysis Visit Windows for Safety and Efficacy Assessments			
Assessment	Visit¹	Target Study Day	Analysis Visit Window (in study days)^{2, 3, 4, 5}
Sweat Chloride Lung Clearance Index (LCI)	Day 1 (Baseline)	1	≤1 Pre-dose
	Day 15	15	(1, 22]
	Week 4	29	(22, 43]
	Week 8	57	(43, 85]
	Week 16	113	(85, 141]
	Week 24	169	(141, 183]

¹ Visit name for analysis purpose is used to report data in tables and figures.

² The analysis visit windows will be applied using the following rules for both scheduled and unscheduled visits:

- a. If no numerical measurement is available within a visit window, the measurement will be considered missing for the visit.
- b. If there is more than 1 numerical measurement available within a visit window, use the following rules:
 - i. The measurement closest to the target day will be used; or
 - ii. If there are multiple measurements with the same distance from the target day, the latest measurement will be used. If the latest measurement cannot be determined, then unscheduled visit will be selected

³ For measurements collected on the date of first dose of study drug, if it cannot be determined whether the measurement is before or after the first dose:

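### Should a COVID-19 catch-up value taken after dosing has ended be kept out of the Week 24 analysis?

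*SAP*

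**What the plan says.** SAP 9.1 (General Considerations) places unscheduled measurements "In scheduled visit windows per specified visit windowing rules". Table 12-1 in SAP Appendix A gives the Week 24 window for LCI and SwCl as after Day 141 up to and including Day 183, with target Day 169. Footnote 2 opens "The analysis visit windows will be applied using the following rules for both scheduled and unscheduled visits" and takes the measurement nearest the target day. Nothing in the table refers to the last dose.

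Protocol 9.6.1 says of the end of dosing: "The last dose of study drug will be the evening dose administered the day before the Week 24 Visit". Protocol Table 3-2 gives the dosing span as "Day 1 through evening before Week 24 Visit".

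Version 3.0 of the COVID-19 addendum, which names this study, provides for unscheduled visits that "may be conducted at any time during the study (including after the protocol defined last study visit"; the condition is "in the event assessments specified to be collected at a scheduled visit were not collected due to COVID-19".

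SAP 9.3.1.2 averages the treatment difference over Weeks 4, 8, 16 and 24, and SAP 9.3.2.2 uses the same model for SwCl. Neither restricts the data to on-treatment values. SAP 9.4.8 provides a listing of visits affected by COVID-19.

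**The concern.** For a subject who keeps to the schedule, the Week 24 measurement falls one day after the last dose. Suppose instead that dosing ended as planned but the LCI2.5 or SwCl measurement was missed because of COVID-19. A catch-up test by Day 183 is then labelled Week 24, although the subject may have been without study drug for two weeks or more. If benefit wanes off drug, the active-arm mean at Week 24 moves toward placebo, and so does the primary estimate. The gap in such a value comes from the planned end of dosing plus a logistic delay, not from a failure of the assigned treatment. That makes it reasonable to ask whether it belongs in the Week 24 contrast, and whether the SAP should settle the matter before unblinding.

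**Working it through.** **Inputs.** Difference -1.0, SD 1.5, 49 completers per group, two-sided 5% t-test (Protocol 12.1, SAP 7.2). Week 24 target Day 169 and window to Day 183 (SAP Table 12-1). Visit tolerance of 5 days either way (Protocol Table 3-2). Week 24 weight of 1/4 (SAP 9.3.1.2).

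**Planned power.** The noncentral t gives 90.4% with 49 per group (89.8% with 48), which agrees with the stated figure of approximately 90%.

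**Time off drug.** Last dose day = visit day - 1. The earliest catch-up is the day after the visit, 2 days after the last dose. The latest is Day 183, which is 183 - (visit day - 1) days after it.

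| Week 24 Visit | Last dose | Catch-up days in window | Days after last dose |
|---|---|---|---|
| Day 164 | Day 163 | 165 to 183 | 2 to 20 |
| Day 169 | Day 168 | 170 to 183 | 2 to 15 |
| Day 174 | Day 173 | 175 to 183 | 2 to 10 |

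These intervals apply only if dosing stopped at the planned visit. If the visit itself was delayed and dosing continued up to it, there is no extra gap.

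**Dilution.** Let f be the share of active-arm Week 24 values affected and L the share of the contrast lost in them. The documents give neither, so both are assumed. Week 24 difference = -(1 - fL). Four-visit average = [3 x (-1) - (1 - fL)]/4 = -(1 - fL/4). Power uses SD 1.5 and 49 per group.

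| f (of 49) | L = 50%: average, power | L = 100%: average, power |
|---|---|---|
| 0 | -1.0, 90.4% | -1.0, 90.4% |
| 5% (about 2) | -0.99375, 90.1% | -0.9875, 89.7% |
| 10% (about 5) | -0.9875, 89.7% | -0.975, 89.0% |
| 20% (about 10) | -0.975, 89.0% | -0.95, 87.4% |

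For SwCl, take as an assumption the -41.8 mmol/L reported in Protocol 9.3.3 for subjects aged 12 and over. Full loss in 5%, 10% and 20% then gives -41.8 x 0.9875 = -41.3, -41.8 x 0.975 = -40.8 and -41.8 x 0.95 = -39.7.

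**What exclusion would cost.** Take five visits with equal correlation rho and a share f of Week 24 values missing at random. The standard error of the four-visit average rises by these factors:

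| f | rho = 0.5 | rho = 0.8 |
|---|---|---|
| 5% | 1.0016 (power 90.35%) | 1.0005 (90.41%) |
| 10% | 1.0033 (90.25%) | 1.0010 (90.38%) |
| 20% | 1.0075 (90.02%) | 1.0023 (90.31%) |

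The loss from the reference 90.43% is at most about 0.4 points. Precision therefore does not decide the matter: dilution and exclusion both have small effects over these ranges. The choice turns on which values the analysis is meant to use.

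**Which values the plan uses.** Protocol 9.1.2 and 9.1.4 keep early discontinuers in the study through all remaining visits. SAP 8.2 analyses subjects as randomized, and SAP 9.3.1.2 applies no dosing filter. Values taken weeks or months off drug are thus in the model already. Windowing by study day is consistent with that.

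**The case for a change.** The strongest case for a change is that an early discontinuer and a completer differ. The discontinuer's off-drug value is a consequence of the assigned treatment, whereas the completer's is an artefact of scheduling. The visible SAP names no treatment-policy strategy that would cover both. Values lost to travel limits are plausibly missing at random, the SAP already derives a last dose date, and a days-since-last-dose limit would keep values from subjects who dosed up to a delayed visit. Where contrast really is lost, exclusion costs less power than dilution in the scenarios above. LCI2.5 also looks the more exposed endpoint: the visible text of addendum Version 1.0 lists sweat chloride among in-home assessments but not multiple-breath washout (parts are redacted).

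The factual part stands: the rule is by study day, and it does not look at dosing. Four points limit what follows from it.

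- **Few subjects qualify.** Dosing must have ended, the measurement must be missing because of COVID-19, and the subject must return by Day 183. Dosing is tied to the visit, and the addendum gives as its reason for direct drug shipment "To ensure subjects can continue treatment with study drug without interruption while ensuring their safety".
- **The direction is not established.** Dilution requires benefit to wane within 2 to 20 days, and the documents contain no washout data.
- **A cutoff has its own faults.** The documents offer nothing from which to set the number of days. At 15 or more it changes nothing for an on-target visit. At 2 it could remove an on-time Week 24 value from a completer who missed the last doses. It would also drop completers' values while keeping those of subjects who stopped much earlier.
- **Open-label exposure is uncertain.** Under Protocol 9.1.6, participation ends at Week 24 for completers who "enter an open-label extension safety study within 28 days of the Week 24 Visit: the Week 24 Visit". Whether a later value would enter this study's data is not settled by the text and cannot support a change.

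**Conclusion.** No change is needed; this is a fair trade-off. Followed as written, the plan gives one clear answer: a completer's catch-up value inside the window counts as Week 24. That agrees with how the model treats other off-drug data and with the purpose of the catch-up visits, which is to recover efficacy assessments that would otherwise be lost.

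If benefit wanes quickly, the result is slightly conservative. At f = 10% and L = 50% the average moves by 0.0125 and power by 0.7 points. At f = 20% and total loss they move by 0.05 and 3.0 points. Total loss is an extreme for values that may be only 2 days past the last dose. Because the dilution is toward no difference, it does not put the type I error rate at risk.

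These sizes rest on assumed f and L, an unchanged SD of 1.5 for the four-visit average, and 49 analysed subjects per group. Part of the SAP's efficacy section is redacted and may hold related supportive analyses, but the visible Appendix A governs visit assignment either way. With the COVID-19 listing and the derived last dose date, analysts can identify affected values and check sensitivity to them if the numbers prove larger than expected.

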Appendix B: Imputation Rules for Missing Prior/Concomitant Medication Dates

Imputation rules for missing or partial medication start/stop dates are defined below:

1. Missing or partial medication start date:
 - a. If only DAY is missing, use the first day of the month.
 - b. If DAY and Month are both missing, use the first day of the year.
 - c. If DAY, Month and Year are all missing, use a date before the first dose date (in practical, use the inform consent date to impute).
2. Missing or partial medication stop date:
 - a. If only DAY is missing, use the last day of the month.
 - b. If DAY and Month are both missing, use the last day of the year.
 - c. If DAY, Month and year are all missing, assign ‘continuing’ status to stop date (in practical, use the end of study date to impute).

In summary, the prior, concomitant, or post categorization of a medication is described below.

Table 12-2 Prior, Concomitant, and Post Categorization of a Medication

Medication Start Date	Medication Stop Date		
	< First Dose Date of Study Drug	≥ First Dose Date and ≤ End Date of TE Period	> End Date of TE Period
< First dose date of study drug	P	PC	PCA
≥ First dose date and ≤ End date of TE period	-	C	CA
> End date of TE period	-	-	A

P: Prior; C: Concomitant; A: Post

Imputation rules for missing and/or partial dates of non-pharmacological treatment/procedure will follow the same imputation rule.

Appendix D: Imputation Rules for Missing AE dates

Imputation rules for missing or partial AE start date are defined below. If the imputed AE start date is before the informed consent date, the AE start date will be imputed using the study informed consent date.

- **If only Day of AE start date is missing:**

- If the full (or partial) AE end date is NOT before the first dose date of the Treatment Period or AE end date is missing, then
 - if AE start year and month are equal to the month and year of first dose date of the Treatment Period, then impute the AE start day as the day of first dose date of the Treatment Period;
 - else impute the AE start day as 1.
- else impute the AE start day as 1.

Compare the imputed AE start date with TE period to determine whether the AE is pretreatment AE, TEAE, or post-treatment AE.

- **If Day and Month of AE start date are missing:**

- If the full (or partial) AE end date is NOT before the first dose date of the Treatment Period or AE end date is missing, then
 - if AE start year is equal to the year of first dose date of the Treatment Period, then impute the AE start month and day as the month and day of first dose date of the Treatment Period;
 - else impute the AE start month as January and day as 1.
- else impute the AE start month as January and day as 1.

Compare the imputed AE start date with TE period to determine whether the AE is pretreatment AE, TEAE, or post-treatment AE.

- **If Year of AE start date is missing:**

If the year of AE start is missing or AE start date is completely missing then query site and

- If the full (or partial) AE end date is NOT before the first dose date of the Treatment Period or AE end date is missing, then impute the AE start date as the date of first dose date of the Treatment Period.
- else impute AE date as the informed consent date.

The imputation should ensure the imputed AE start date is not before the informed consent date.

Imputation rules for partial AE end date are defined below:

- If partial end date, then impute as min (the last day of the month, end of study participation) if day is missing, or min (Dec, end of study participation) if month is missing.

